16.4. Multiple Comparisons/Multiplicity

Analysis of the primary efficacy endpoint, medically-significant RSV LRTI in infant subjects, will be performed following a hierarchical closed procedure to control for the overall Type I error rate at 1-sided 0.025. A demonstration of vaccine efficacy through the first 90 days at a Type I error rate of 0.0124 (i.e., lower bound of two-sided 97.52% CI above the pre-specified threshold) will be required prior to testing of subsequent time-points, through 120, 150, and 180 days at Type I error rate of 0.025 (i.e., lower bound of two-sided 95% CI above the pre-specified threshold). Two sets of parallel analyses will be performed for the primary efficacy endpoint, one set for the US-FDA and the other for the ex-US global regulatory submissions (e.g., EMA and WHO) using different success criteria for the primary endpoint, H_0 : Vaccine Efficacy $<$ 30% for the US-FDA and H_0 : Vaccine Efficacy \leq 0% for the ex-US global regulatory submissions. The two sets of analyses will be the same for all other statistical approaches (i.e., methods of analysis, Type I error adjustments, and hierarchical testing approach).

Analysis of secondary and exploratory efficacy endpoints and immunogenicity endpoints will be performed without adjustment for multiple comparisons. The final interpretation of the total vaccine efficacy and the duration of protection will be based on the totality of statistical evidence including immunogenicity results and pre-specified exploratory endpoints; and the clinical importance in discussions with the regulatory agencies and scientific communities.

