4.1.2. Secondary Objectives

The secondary objectives of this study are:

- To determine the efficacy of maternal immunization with the RSV F vaccine in reducing the incidence in infants of:
 - RSV LRTI with EITHER severe hypoxemia (SpO_2 < 92% at sea level or < 87% at altitudes > 1800 meters) or the documented use of oxygen by high flow nasal cannula OR a requirement for continuous positive airway pressure (CPAP) or bilevel positive airway pressure (BiPAP) OR Bubble CPAP OR bag-mask ventilation OR intubation with subsequent mechanical (or manual) ventilation OR extracorporeal membrane oxygenation (ECMO), through the first 90 days of life in infants of maternal RSV F vaccinees as compared to placebo recipients. In the event that efficacy is shown through the first 90 days of life, a hierarchical sequence of hypothesis tests will be carried out to examine efficacy at 120, 150, and 180 days of life.
 - RSV LRTI leading to hospitalization through the first 90 days of life in infants of maternal RSV F vaccinees as compared to placebo recipients. In the event that efficacy is shown through the first 90 days of life, a hierarchical sequence of hypothesis tests will be carried out to examine efficacy through 120, 150, and 180 days of life.

The two secondary efficacy objectives will be evaluated in term infants (≥ 37 weeks gestational age at delivery) born to maternal subjects who received a study injection ≥ 2 weeks (14 days) prior to delivery. Infants with multiple RSV episodes meeting a given criterion will be counted

only once, using data from the first episode. Success under the secondary efficacy hypotheses will be achieved by demonstration of a lower bound of a two-sided 95% confidence interval for the estimate of vaccine efficacy which exceeds 0%.

- To describe the immunologic responses to the RSV F vaccine in healthy maternal subjects, in the third trimester of pregnancies deemed to be at low risk of obstetrical complications, through delivery and six months thereafter.
- To describe the transplacental transfer of maternal antibodies specific for RSV and its F protein based on the ratio of levels in maternal and cord blood at delivery.
- To estimate the rate of decay of RSV and F protein-specific antibodies in infants through the first six months of life.
- To develop an immune correlate of risk of the RSV LRTI syndromes in infants based on anti-F protein antibody and/or palivizumab-competitive antibody levels measured in the infant and/or cord blood.

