10.4. Analysis of Secondary Efficacy Objective

Analysis of secondary efficacy endpoints will be using the frequentist method. The relative risk (RR) and its two-sided 95% CI will be estimated using Poisson regression with robust error variance [Zou 2004]. A generalized linear model with unstructured correlation matrix (robust error variances) will be used. The explanatory variables in the model will include the treatment group. The dependent variable will be the incidence rate. The Robust error variances will be estimated using repeated statement and the subject identifier. Poisson distribution will be used with a link function logarithm. The vaccine efficacy and the corresponding two-sided 95% CI will be calculated.

The null hypothesis, $H_0: VE \leq 0\%$, using the 1-sided Type I error rate (i.e., lower bound of two-sided 95% CI) will be used for analyses of all secondary efficacy endpoints in infants. For each endpoint, in the event that efficacy is shown through the first 90 days of life, a hierarchical sequence of hypothesis tests will be carried out to examine efficacy through 120, 150, and 180 days of life.

Additional efficacy analyses may describe the incidence of symptoms used to define RSV LRTI. Percentages of infant subjects with any RSV-confirmed respiratory illness accompanied with the following events/complaints may be presented by treatment group through six months postpartum: cough, nasal flaring, difficulty breathing, manifesting in any of the following clinical signs or symptoms as lower chest wall indrawing, subcostal retractions, abnormal breath sounds (inclusive of stridor, rales, rhonchi, wheezing, and crackles/crepitations), and/or observed apnea. Time to the first RSV-associated event referenced above will also be analyzed using Kaplan-Meier methods for each event category and by treatment group.

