16. DATA HANDLING CONVENTIONS

All statistical analyses will be 2-tailed and assessed at the 5% significance level.

All output will be incorporated into Microsoft Word (including rtf format) or Excel files, or Adobe Acrobat PDF files, sorted and labeled according to the International Conference on Harmonization (ICH) recommendations, and formatted to the appropriate page size(s).

Tabulations will be produced for appropriate demographic, baseline, and safety parameters. For categorical variables, summary tabulations of the number and percentage of subjects within each category (with a category for missing data) of the parameter will be presented. For continuous variables, the number of subjects, mean, median, standard deviation (SD), minimum, and maximum values will be presented.

For all analyses, a two-sided p-value of < 0.05 (one-sided p-value < 0.025 where appropriate) will be considered statistically significant except for the primary efficacy endpoint, medically significant RSV LRTI through 90 day that will be evaluated using a one-sided p value of 0.0124

All references to analysis of GMEU/GMC/ GMT will be interpreted as analysis of the log (base 10) of EU or concentration values or of the reciprocal titers (e.g., the reciprocal titer of 1:160 is the number 160). Values recorded as below the lower limit of quantitation (LLOQ) of the assay for PCA and anti-F IgG will be set to half LLOQ for the purposes of GMEU/GMC, and GMFR analyses. For MN assays, titers will be reported in International Unit (IU) with the LLOQs of 13 for RSV/A and 8 for RSV/B. Titers below the LLOQs will also be set to half LLOQ, 6.5 IU for RSV/A and 4 IU for RSV/B.

For all data analyses and summary tabulations, categories for analysis and presentation will consist of the RSV F vaccine treatment groups. All descriptive statistical analyses will be performed using SAS statistical software Version 9.3 or higher in a Windows environment, unless otherwise noted. Medical history and AEs will be coded using the MedDRA Version 16.1.

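### Each of the two secondary efficacy endpoints has its own success rule at one-sided 0.025, with no adjustment, order or gate on the primary; the chance of a false secondary success can rise from 2.5% to at most about 4.9%

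*SAP*

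**What the plan says.** SAP 4.1.2 names two secondary efficacy endpoints through Day 90: "RSV LRTI with EITHER severe hypoxemia" (or listed forms of respiratory support), and "RSV LRTI leading to hospitalization through the first 90 days of life". It then gives them a decision rule: "Success under the secondary efficacy hypotheses will be achieved by demonstration of a lower bound of a two-sided 95% confidence interval" lying above 0% vaccine efficacy (VE). Protocol 2.2 and the synopsis carry the same rule.

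SAP 10.4 tests each against a null of VE at or below 0%, "using the 1-sided Type I error rate (i.e., lower bound of two-sided 95% CI) will be used for analyses of all secondary efficacy endpoints". Section 10.4 does not print the level. It follows from the interval, and SAP section 16 gives the general level as "one-sided p-value < 0.025 where appropriate".

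The only gate on the secondaries lies inside each one: "For each endpoint, in the event that efficacy is shown through the first 90 days of life, a hierarchical sequence of hypothesis tests" follows at 120, 150 and 180 days.

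SAP 16.4 sets a closed hierarchy for the primary endpoint at an overall one-sided 0.025: Day 90 at 0.0124, then the later time points at 0.025. It says that secondary, exploratory and immunogenicity analyses "will be performed without adjustment for multiple comparisons", and adds that final interpretation will rest on all the evidence, in discussion with regulators. SAP section 10, by contrast, presents the primary's closed procedure as controlling Type I error *for the study*.

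**The concern.** A rule that defines success reads as a confirmatory claim. The objectives reinforce this: the secondary efficacy objectives are there to determine efficacy, whereas the exploratory ones are there to describe it and have no success rule. Yet no error rate is controlled across the two secondary tests, and neither waits for the primary.

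This matters because a missed primary is a realistic outcome in the US-FDA set, where the null is VE below 30% at one-sided 0.0124. The secondaries face an easier null (0%) at a looser level (0.025). A failed primary beside a declared secondary success is therefore possible under the plan, and the plan does not say what such a success would mean. The section 10 sentence makes it worse, because a reader could take it to cover the secondaries too.

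**Working it through.** **1. The plan's own figures.** The documents give no family-wise error rate for the secondaries, so the check starts with the primary's level and power.
- Interval level: 1 − 2 × 0.0124 = 0.9752, matching the stated 97.52%.
- Power (SAP section 13: 2,786 vaccine and 1,432 placebo infants, placebo rate 4%, VE 65%). The vaccine rate is 0.35 × 0.04 = 0.014. The variance of log RR is 0.986/(2,786 × 0.014) + 0.96/(1,432 × 0.04) = 0.0253 + 0.0168 = 0.0420, so SE = 0.205. Then ln(0.70/0.35)/0.205 = 3.38. Subtracting the critical value 2.24 leaves 1.14, and Φ(1.14) is about 87%. The stated figure is 87%.

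**2. Level of each secondary test.** (1 − 0.95)/2 = 0.025 one-sided, critical value 1.96.

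**3. At least one false Day 90 secondary success, both nulls true.**
- Independent: 1 − (1 − 0.025)² = 0.0494. The Bonferroni bound is 0.025 + 0.025 = 0.050.
- Correlated: 1 − Φ₂(1.96, 1.96; ρ), where Φ₂ is the bivariate normal distribution function. The documents give no ρ, so a range is shown.

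| ρ | Chance of a false success | Ratio to 0.025 |
|---|---|---|
| 0 | 4.94% | 1.98 |
| 0.3 | 4.76% | 1.91 |
| 0.5 | 4.54% | 1.82 |
| 0.7 | 4.17% | 1.67 |
| 0.9 | 3.52% | 1.41 |

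**4. Which part of the range is plausible.** SAP 4.2.2 requires the same RT-PCR confirmation and the same list of LRTI signs for both endpoints, and takes in-hospital respiratory support from hospital records. Positive correlation is therefore expected. A simulation at the planned arm sizes assumed hospitalization rates of 2–3% and severe-hypoxemia rates of 1–2%:
- 75% of severe cases also hospitalized: 4.3–4.9%.
- All severe cases hospitalized, hospitalization the commoner endpoint: 4.1–4.6%.
- The two endpoints coincide: 2.6%.
- Only 25% overlap: 5.1–5.2%. Here each test alone rejects in 2.6–2.7% of trials, so the excess over 4.9% comes from the approximate test at low event counts and not from multiplicity.

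**5. Later time points.** An endpoint's 120-, 150- and 180-day tests run only after its own Day 90 success. With no effect at Day 90, a false success has already occurred before the chain opens, so the chain adds nothing to the figures above.

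**6. If the section 10 sentence is read literally.** The Day 90 primary (null VE at or below 0%, at 0.0124) and both ungated secondaries give 1 − 0.9876 × 0.975² = 6.12% if independent, 5.33% at ρ = 0.5 and 4.68% at ρ = 0.7.

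**7. What the remedies achieve.**
- Gate on the Day 90 primary alone (null VE at or below 0%): at most 1.24% for any false claim when nothing works. When the primary effect is real the gate opens, and the two secondaries are back at the figures in step 3.
- Holm on the two Day 90 tests (0.0125 for the smaller p-value): 1 − 0.9875² = 2.48% if independent, 2.32% at ρ = 0.5, 2.15% at 0.7 and 1.81% at 0.9.

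**The case against.** The best defence is that this is a disclosed choice. SAP 16.4 says plainly that the secondaries are unadjusted, limits its overall 0.025 to the primary endpoint, and leaves the final reading to the totality of evidence. Each secondary is tested at its own stated level, and the plan never promises a family-wise 0.025 across them. The section 10 sentence names only the primary endpoints and refers the reader to 16.4.

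Much of this stands. There is no arithmetic error and nothing is concealed. It does not explain why tests described as unadjusted also carry a success rule, or what that success means if the primary fails.

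Three stronger readings are tempting, and the documents do not support them:
- *The false-success rate nearly doubles.* That is the independence case. The endpoints share their virological and clinical criteria, so 4.9% is close to a ceiling.
- *The 120-, 150- and 180-day chains inflate the error further.* They are gated within each endpoint and do not.
- *The primary's error control is compromised.* The primary is tested in its own hierarchy whatever the secondaries show.

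**Conclusion.** The structural point holds: two formal success rules at one-sided 0.025, no adjustment, no order, and no dependence on the primary. With both nulls true, the chance of at least one false Day 90 secondary success can rise from 2.5% to at most about 4.9%, and is more plausibly 3.5–4.8% for correlations of 0.9 down to 0.3. This assumes that each test holds its nominal level and that the correlation is not negative; the correlation itself is an assumption.

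The numerical inflation is moderate. The more important consequence is interpretive: the plan permits a declared secondary success after a failed primary, next to a sentence that can be read as error control for the whole study. This should be corrected, but it does not threaten the primary analysis.

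**What to change.** **Preferred: report the secondaries as nominal.**
- State in SAP 16.4 that the secondary efficacy results are nominal and unadjusted.
- Remove the success rule from Protocol 2.2, the protocol synopsis and SAP 4.1.2, keeping the estimates and 95% intervals.
- Limit the *for the study* phrase in SAP section 10 to the primary endpoint.

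This agrees with what 16.4 already says. It costs wording in both documents, including a protocol amendment, and should be done before the Day 180 unblinding. It needs no new data or sample size.

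**If formal secondary claims are wanted.** Open them only after the Day 90 primary succeeds in the relevant regulatory set (null VE < 30% for the US-FDA, VE ≤ 0% ex-US). Then place the two Day 90 secondaries, the primary's 120-, 150- and 180-day tests and the secondaries' own later tests in one pre-specified sequence, or split alpha among them, for example by Holm. Opening the secondaries at 0.025 after the gate is not enough, because the primary's later tests already use 0.025 there. Two true nulls tested in parallel at that level bring back up to 4.94%. The order of the two secondaries would have to be chosen, since the documents do not rank them.

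The cost of this route is that, in a single sequence, results after the first miss are nominal only. In the US-FDA set that may be common: SAP Table 3 gives primary power of 26–34% at VE 50% for placebo rates of 3–4%, so the gate would stay shut in 66–74% of such trials.

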16.5. Withdrawals, Dropouts, Loss to Follow-up

The Investigator may, at his/her discretion, restrict a maternal or infant subject from receiving study treatment or other study procedures if he/she considers it to be in the maternal or infant subject's best interest to do so, but can suggest that the maternal or infant subject remain in the study to be followed for safety if the maternal subject has received a test article. In this situation, the reason for not performing the study treatment and/or procedure should also be recorded as a protocol deviation and clearly documented in the source document.

In the event of early termination, Investigators will make every reasonable effort to perform study completion procedures. Subjects (maternal and infants) who terminate from the study early will not be replaced. See Sections 6.4 to 6.6 of the protocol for more details on withdrawal of subjects.

16.6. Missing, Unused, and Spurious Data

In general, there will be no substitutions made to accommodate missing data points. All data recorded on the eCRF will be included in data listings that will accompany the CSR.

For maternal subjects, if delivery date is missing, it will be imputed as the estimated delivery date (EDD) to establish the projected end time for their efficacy analysis.

When tabulating AE data, partial dates of AE onset will be handled as follows:

- If the day of the month is missing, the onset date will be assumed to be the date of either the first, in order to conservatively report the event as vaccine-emergent, unless the month reported clearly indicates the event would be outside the window for vaccine-emergent events, in which case no date will be imputed.
- If the onset day and month are both missing, the event onset will be coded to the day of vaccination (the birth date for infant subjects) in order to conservatively report the event as vaccine-emergent, unless it is clear by reference to the year that the event is outside the window for vaccine-emergent events.
- A completely missing onset date will be coded as the day of vaccination.

A conservative approach will be taken to assess the relationship of an AE to vaccine: if the relationship of an event is missing, it will be considered treatment-related. Missing severity for an AE will not be imputed.

When determining whether the concomitant medication was taken post-vaccination (i.e., start date is on or after the vaccination date), missing or incomplete start date will be handled as follows:

- If the start date is completely missing and the reason for use is not marked as preexisting, it will be treated as post-vaccination.
- If only the year is provided and the year is on or after the year of the vaccination and the reason for use is not marked as preexisting it will be treated as post-vaccination.
- If only the year and month are provided and the year and month are on or after the year and month of the vaccination and the reason for use is not marked as preexisting it will be treated as post-vaccination.

When tabulating concomitant medications data associated with the RSV surveillance illnesses, partial or missing dates of start and stop will be handled as follows:

- If a start date is completely missing, it will be assigned as Day 14 (start of the RSV surveillance for each subject) for maternal subjects (the birth date for infant subjects).
- If a stop date is missing, it will be assigned Day 180 post-delivery (end of the RSV surveillance for all subjects).
- If the day and month are missing for a start date, it will be assigned 01 January of the year or Day 14 for maternal subjects (the birth date for infant subjects) whichever is the latest.
- If the day and month are missing for a stop date, it will be assigned Day 180 post-delivery (end of the RSV surveillance for all subjects) or December 31 of the year whichever is the earliest.

- If the day is missing for a start date, it will be assigned the 1st day of the month or Day 14 (start of the RSV surveillance for each subject) for maternal subjects (the birth date for infant subjects) whichever the latest.
- If the day is missing for a stop date, it will be assigned the last day of the month or Day 180 post-delivery (end of the RSV surveillance for all subjects), 01 May for 2016 or December 31 of the year whichever is the earliest.

When determining preterm birth categories (Very preterm and Moderate to late preterm), if the study EDD is missing other available data (e.g. LMP or third trimester ultrasound, or GA at birth reported on the SAE narrative) will be used to determine the GA at birth.

When tabulating RSV surveillance illness episodes, onset or end date will be determined as follows:

- Parent-reported illness start date and return to normal date will be used as the start/end date for an episode.
- In the case of a missing or incomplete start date or return to normal date:
 - If start date is missing: impute the start date by the first contact date when parent reported symptoms or the first on-site visit date when site observed symptoms (whichever is earlier).
 - If return to normal date is missing: impute the return to normal date by the last contact date when parent reported symptoms or the last on-site visit date when site observed symptoms (whichever is later).
- If there is a “2~3 days after initial” visit record after the episode end date AND the record indicates site-observed symptom(s), adjust the episode end date to coincide with on-site visit date (episode will be extended).
- Each hospital stay is considered a single illness episode.
- If a parent-reported outpatient illness episode overlaps with a hospital stay, or extends to the onset of a hospital stay, or begins at the end of a hospital stay, then the episodes will be merged using the earliest of episode start or hospital admission as the start date and the latest of the hospital discharge or parent-reported episode end date as the end date.
- If 2 illness episodes occur within 7 days (≤ 6 days), combine them to form a single illness episode (two episodes will be combined into one).
- Additional imputations may be performed by a Novavax medical staff if warranted in a blinded fashion.

When respiratory hospitalization admission and discharge dates for an infant subject are missing (or incomplete), they will be determined as follows:

- If the day of the month is missing:
 - The admission date will be imputed as the 1st of the month or the start date of the corresponding SAE whichever is later.
 - The discharge date will be imputed as the last of the month or the end date of the corresponding SAE whichever is earlier.
- If both the day of the month and the month are missing:
 - The admission date will be imputed as the 1st of January or the start date of the corresponding SAE whichever is later.
 - The discharge date will be imputed as the 31st of December or the end date of the corresponding SAE whichever is earlier.
- If the year is missing, the admission date or the discharge date will be imputed as the onset or the end date of the corresponding SAE, respectively.

Meeting all of the following conditions will be required to link a RSV surveillance illness episode and a concomitant medication:

- Answer to “Did subject take any medications/treatments for these symptoms?” on the RSV Surveillance CRF is marked as “Yes”.
- The reason for taking the medication is marked as “Respiratory Surveillance” or “Unsolicited Adverse Event”. If it is marked “Unsolicited Adverse Event”, a manual review of the reported medications by clinician to confirm the link.
- Medication start date is not later than the illness end date.
- Medication stop date is on or after the illness onset date.

The following data conventions will be used for handling serology samples with respect to collection windows and missing or incomplete collection dates.

- If delivery time and dates are missing or incomplete to calculate the sample collection windows for samples at delivery, the CRF visit information will be used without applying the collection window. Cord blood samples identification will be based on the CRF visit information without applying the window and the cord blood if collected will be used for all analyses as the delivery sample.
- Delivery sample windows are defined as -24 to 72 hours from delivery for infants and -72 to 72 hours from delivery for maternal subjects.
- For each visit, one sample with the closest to the scheduled visit date will be selected for the analysis.

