12. SAFETY ANALYSES

Adverse events are defined as any unfavorable or unintended change in the physical, psychological, or biochemical condition of the subject. An AE temporally related to participation in the study will be documented whether or not considered related to the test article. This definition includes intercurrent illnesses and injuries, and exacerbations of pre-existing conditions. Stable pre-existing conditions which do not change in nature or severity during the study are not considered AEs; however, these should be collected as part of the medical history. AEs will be considered treatment emergent from the date and time of the first administration of the investigational product. All safety and reactogenicity summaries will be based on the Safety Population.

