12.4. Unsolicited Adverse Events

Any AEs reported by maternal subjects will be categorized as unsolicited events and Medical Dictionary for Regulatory Activities (MedDRA) coded by system organ class (SOC) and preferred term (PT). Solicited events with an onset after the solicitation period will also be classified as unsolicited AEs. Unsolicited events that occur within 7 days following vaccination should also be recorded in the subject diary. If any grade 3 unsolicited event is reported during this period, maternal subjects should be encouraged to contact the investigator by telephone. The investigator may request an *ad hoc* clinic visit at his/her judgment, and should enter any grade 3 unsolicited adverse event reported by telephone in the unsolicited AE eCRF promptly, even if the balance of diary data is not yet available. Continuing non-serious solicited AEs lasting beyond the 7-day diary period reported on the AE CRF to collect the symptom end date will not be summarized in the unsolicited AE tables. Solicited AEs reported on the AE CRF will be treated as solicited AEs and will be summarized in solicited AE tables only.

Any AEs reported in infants will be categorized as unsolicited events and MedDRA coded by SOC and PT. These can include, but are not limited to, abnormalities in vital signs, metabolic screening and developmental tests, neonatal hearing, congenital anomalies, respiratory failure, perinatal infections, neonatal death, complications that result in extended hospitalization; as well as any other SAE (as defined in Section 8.5 of the Protocol) or MAE or SNMC (as defined in Section 8.4 of the Protocol).

All unsolicited AEs will be assessed for severity and for causality for infants and maternal subjects.

The following summaries of unsolicited AEs will be presented for all maternal subjects in the Safety Population as part of the secondary analysis of safety:

- Overall summary of unsolicited AEs by treatment group (Day 0 post-vaccination to Day of delivery -1 and also Day 0 post-vaccination to Delivery +180).
- A summary by severity (mild, moderate, or severe), MedDRA SOC, PT, and treatment group (Day 0 post-vaccination to D+180).
- A summary by relationship to study vaccine, MedDRA SOC, PT, and treatment group (Day 0 post-vaccination to D+180).
- A summary of severe and related AEs, MedDRA SOC, PT, and treatment group (Day 0 post-vaccination to D+180).

For infants, the following summaries of unsolicited AEs will be presented:

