- An overall summary of unsolicited AEs (Delivery to Delivery + 180 days and/or Delivery + 364 days).
- A summary by severity (normal, mild, moderate, or severe), MedDRA SOC, PT, and treatment group (Delivery to Delivery + 180 days and/or Delivery + 364 days).
- A summary by relationship to study vaccine, MedDRA SOC, PT, and treatment group (Delivery to Delivery + 180 days and/or Delivery + 364 days).
- A summary of severe and related AEs, SAEs, MAEs, and SNMCs, by MedDRA SOC, PT, and treatment group (Delivery to Delivery + 180 days and/or Delivery + 364 days).

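### The missing-day rule for adverse event onset in SAP 16.6 is cut short and has no floor at vaccination or birth, so, read literally, it can date early events before the safety tables begin

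*SAP*

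**What the plan says.** SAP 16.6 has three bullets on partial AE onset dates.

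- Day missing: "the onset date will be assumed to be the date of either the first, in order to conservatively report the event as vaccine-emergent". One exception follows: "unless the month reported clearly indicates the event would be outside the window for vaccine-emergent events, in which case no date will be imputed".
- Day and month missing: "the event onset will be coded to the day of vaccination (the birth date for infant subjects"), again unless the year places the event outside the window.
- Everything missing: "A completely missing onset date will be coded as the day of vaccination". No separate anchor is given for infants.

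These dates feed tables with fixed starting points. SAP 12 states that "AEs will be considered treatment emergent from the date and time of the first administration of the investigational product". In SAP 12.4 the overall maternal summary covers "Day 0 post-vaccination to Day of delivery -1 and also Day 0 post-vaccination to Delivery +180". The first infant summary there is "An overall summary of unsolicited AEs (Delivery to Delivery + 180 days and/or Delivery + 364 days"), and the other infant summaries use the same delivery-based window.

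Other rules in SAP 16.6 do carry a floor. For medications linked to surveillance illnesses, "If the day is missing for a start date, it will be assigned the 1st day of the month or Day 14" for mothers, or the birth date for infants, taking whichever is latest. For respiratory hospital admissions with the day missing, the date is the later of the 1st and the start of the corresponding serious adverse event.

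**The concern.** The only date that the missing-day bullet names is the 1st of the month. If an event happened in the month of vaccination or birth, the 1st will normally come before the injection or the delivery. The exception does not rescue it, because that month is not clearly outside the window. A program that follows the text would date the event before treatment, or before birth, and could exclude it from the summaries that the rule is meant to protect.

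The events at risk are those soonest after injection or birth, where a causal question is most natural. The sentence also cannot be programmed in only one way. One programmer may use the 1st, another may supply the missing alternative, and the two would produce different AE tables from the same data.

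The completely-missing bullet has a related gap. Only the mother is vaccinated, and she is vaccinated before delivery, so an infant event coded to that day is dated before the infant was born.

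**Working it through.** The plan gives no figure for this rule, so there is none to reproduce. The check asks when the literal rule misplaces an event, and how often.

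**Condition.** Let V be the vaccination date (birth date for infants) and let the true onset be on or after V. The imputed date is the 1st of the onset month. It precedes V only if onset is in the same calendar month as V and V is not itself the 1st. In any later month the 1st is after V and the event stays in.

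**Example.** A woman vaccinated on 15 March with an AE dated March is given onset 1 March, 14 days before the injection. An infant born on 15 March with an AE dated March is given an onset 14 days before birth. Under the SAP's post-vaccination rule for concomitant medication, a drug dated March would count as post-vaccination unless marked preexisting, while the event it treated would not.

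**Assumptions, none from the documents.** V is spread evenly over a 30-day month, onset is uniform over the stated window, and the day is missing independently of when onset occurred.

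**Count for early windows.** At a lag of k days, the misplaced cases are those with V on day 2 to day 30 - k, which is 29 - k of the 30 possible days.

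- Days 0-6: 29 + 28 + ... + 23 = 182, out of 30 x 7 = 210, so 182/210 = 87%.
- Days 0-27: (28 x 29) - (0 + 1 + ... + 27) = 812 - 378 = 434, out of 30 x 28 = 840, so 434/840 = 52%.

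**Count over full follow-up.** Lags of 29 days or more add nothing. The total over lags 0-28 is 29 x 30 / 2 = 435, or 435/30 = 14.5 misplaced onset days per subject on average. The horizons come from the infant table windows in SAP 12.4 and, for mothers, from the roughly nine months of participation in SAP 2, taken here as 270 days.

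| Window | 30-day-month count | Calendar enumeration |
|---|---|---|
| Days 0-6 | 182/210 = 87% | 87% |
| Days 0-28 | 435/870 = 50% | 51% |
| Infant, through D+180 | 14.5/181 = 8.0% | 8.1% |
| Mother, about 270 days | 14.5/271 = 5.4% | 5.4% |
| Infant, through D+364 | 14.5/365 = 4.0% | 4.0% |

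The last column crosses every reference date in 2016 and 2017 with every onset day in the window. In that enumeration, 94-96% of events with onset in the same month as V are placed before it. If half of all events fall in Days 0-28 and the rest later, the overall share is 0.5 x 51% + 0.5 x 0% = about 25%.

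**Completely missing date, infants.** No arithmetic is needed. The coded date is the mother's vaccination day, which is before birth, although the bullet just above it uses the birth date.

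**With a floor.** If the imputed date is the later of the 1st and V, it can never precede V, so the share is 0% in every window.

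**The case against.** The strongest reply is that the sentence is visibly damaged and that its purpose clause shows the intent. The lost alternative may well have been the vaccination or birth date, and the neighbouring rules point that way. This stands in part. The SAP does not state that such events are to be dropped. Exclusion is what literal programming would produce. But the text names only the 1st, and an intent that has to be guessed is not a specification.

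A reader might infer that the rule usually puts onset before vaccination or birth. The documents do not support that. AEs are collected for about nine months in mothers and one year in infants, and over those periods the share is about 4-8% under uniform onset. It exceeds half only in roughly the first four weeks, or among events in the reference month.

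Dates in the first week are also likely to be well captured in mothers. The diary is kept daily for Days 0-6 and takes unsolicited events too (Protocol 8.2.1), visits follow at Days 7 and 14, and onset date is a required AE detail (Protocol 8.1). Solicited reactions are tabulated from the diary. The 87% may therefore apply to few events.

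For infants, one might infer that every event with no date is lost. That depends on a programmed cut at delivery. Such an event is still after the mother's injection, so it remains treatment-emergent under SAP 12, and SAP 12.1 frames the infant variable as events since birth. The risk is confined to tables that apply the delivery-onward window to the coded date.

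A diluted difference between arms might also be inferred. With no count of partial dates, that cannot be shown.

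**Conclusion.** The rule is wrong as written. It is incomplete, it lacks a floor, and, followed literally, it works against its own stated aim for events in the month of vaccination or birth. The completely-missing rule has a separate gap for infants.

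The relative size is large for the earliest events (about 87% of day-missing events in Days 0-6, about 52% in Days 0-27) and small over full follow-up (about 4-8%). These shares rest on evenly spread reference dates, uniform onset and a day missing at random. The absolute size is unknown, because the number of partial dates is not given. SAP 16.6 keeps all recorded data in the listings, so no event disappears from the report altogether, and the efficacy analyses do not use this rule. This is a minor to moderate correction. The documents do not support a claim that the safety conclusions are at risk.

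**What to change.** Reword two bullets in SAP 16.6.

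- Day missing: onset is the later of the 1st of the reported month and the vaccination date (birth date for infants), unless the month and year show onset before that date.
- Completely missing: onset is the vaccination date for mothers and the birth date for infants.

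The bullet for day and month both missing can stay. AEs are recorded from consent, so the new wording may count a few maternal events from earlier in the vaccination month as emergent. That is the conservative direction the SAP asks for. The cost is two sentences and a small change to the date-imputation code, with no new data, and it brings the AE rule into line with the floored rules already in the same section.
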